One treatment is defined as 2 consecutive doses (stimulations). Each dose delivers a 2-minute stimulation. One dose is applied to the left side of the neck, then one to the right. If shortness of breath (SOB) persists 20 minutes after start of first treatment, administer a second treatment. If the additional treatments do not appear to be providing benefit/relief of symptoms (as per patient or physician discretion) there is no need to continue with additional acute treatments. However, if it there appears to be benefit, the patient can administer more as needed. The patients can receive up to 9 acute treatments (or 18 stimulations) per day.

SoC: No Administration of gammaCore®

INCLUSION AND EXCLUSION CRITERIA:

Inclusion Criteria

All patients must meet the following inclusion criteria to be included in this study:

1. Patients (age 18 years and older) who have tested positive or suspected/presumed positive for CoViD-19 (PCR real time test)
2. Patients with cough, shortness of breath or respiratory compromise (RR>24/min, increased work of breathing.)
3. O₂ Saturation less than or equal to 96% on room air or sensation
4. Agrees to use the gammaCore Sapphire device as per protocol and to follow all of the requirements of the study including recording required study data
5. Permission for early am blood draw to freeze for subsequent lab tests and sequencing as related to CoViD-19 sequelae
6. Patient is able to provide signed and witnessed Informed Consent

Exclusion Criteria

Patients meeting any of the following criteria cannot be included in this research study:

1. On home/therapy oxygen (i.e. for COPD patients) at baseline prior to development of CoViD-19
2. Already using gammaCore® (nVNS) for other medical conditions
3. A history of aneurysm, intracranial hemorrhage, brain tumors, or significant head trauma
4. Known or suspected severe atherosclerotic cardiovascular disease, severe carotid artery disease (e.g., bruits or history of transient ischemic attack or cerebrovascular accident), congestive heart failure, known severe coronary artery disease, myocardial infarction documented within past 90 days, or current or recent history of life-threatening arrhythmia (sustained ventricular tachycardia, ventricular fibrillation, second or third-degree heart block, uncontrolled atrial fibrillation or

uncontrolled atrial flutter)

5. Patients with clinically significant hypertension, hypotension, bradycardia, or tachycardia (as per investigator discretion)

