6. Current implantation of an electrical and/or neurostimulator device, including but not limited to a cardiac pacemaker or defibrillator, vagal neurostimulator, deep brain stimulator, spinal stimulator, bone growth stimulator, or cochlear implant
7. Current implantation of metal cervical spine hardware or a metallic implant near the gammaCore® stimulation site
8. Belongs to a vulnerable population or has any condition such that his or her ability to provide informed consent, comply with the follow-up requirements, or provide self-assessments is compromised (e.g. homeless, developmentally disabled and prisoner)
9. Compromised access to peripheral veins for blood sampling.
10. Pregnant women
11. Patients with active cancer or those who have had recent cancer treatment

CLINICAL INVESTIGATION PROCEDURE OVERVIEW:

Enrollment / Admission Day - Day 0

Study patient must meet all of the following inclusion criteria and none of the exclusion criteria

- Patient must sign Informed Consent and witness to signature must occur
- Randomization – Upon meeting all eligibility requirements (including verification of +CoViD-19 testing), patient's will be randomized 1:1 into either the control group or the treatment group
- Intake Collection of:
 - Basic Demographics
 - Date of Birth (DOB), Race, Sex, Smoking Status, County/Region
 - Medications, Co-morbidities

- CoViD-19 Test Results (Positive / Presumed Positive)
- Study Measurements:
 - Height/Wt (BMI)
 - Temperature
 - Blood Pressure
 - O₂ Saturation
 - PaO₂/FiO₂ ratio
 - Shortness of Breath (Yes / No)
 - Cough (Yes / No)
- Clinical Labs
 - Immunokine panel (TNF-α, IL-1β, IL-6)
 - Frozen blood sample
 - Leukocyte flow cytometry
 - Pro-Calcitonin
 - CRP
 - Ferritin
 - D Dimer
 - Complete hematology panel (CBC with differential)
 - Comprehensive metabolic panel
 - Serum or urine hCG (for any woman who might be pregnant)
- Device training: Patient receives device training on gammaCore® Sapphire device and receives first treatment with trained study staff*
 - VNS Stimulation Supervised**, record date and times of stimulations
 - Daily Tx Log Completion
 - Oxygen Required, Oxygen level (%) based on device type (HFNC / NC / Bipap / Optiflow), Ventilator Dependence, Date and time of Ventilation, Patient discharge home, Date and time of Discharge, Survival
- Clinical Improvement Ordinal Scale
 - Adverse event assessment

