7.2 Clinical Investigation Procedures and Definitions

Once the patient is admitted to the hospital, the institution shall follow their standard protocol for their CoVid-19 patients. The investigator shall administer the consent form, conduct the intake and randomize the patient 1:1 into each of the two study arms prior to baseline measurements. Once qualified, the patient shall be trained on the use of gammaCore® and provided an initial treatment. For every day the patient is in the hospital but not on mechanical ventilation, the administration of gammaCore®, prophylactically and acutely, will be recorded on the daily study log as per protocol treatment.

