7.2.1 Schedule of Clinical Investigation Events

7.2.1.1 Intake / Admission (Day 0)

Upon hospital admission, after the patient and the Investigator have signed the Informed Consent Form, the patient will be randomized 1:1 into one of the two treatment arms. Patient's severity of condition will be classified based on age, co-morbidities, and oxygen saturation as moderate or severe. To prevent allocation bias, the patient will be assigned to the test or control arm of the study based on severity of classification in a 1:1 ratio. Thereafter, the study physicians and/or attending physicians participating in the study and if feasible, will conduct a complete physical examination and obtain vitals. Medical and demographic information in the EMR pertinent to this trial and the patient's treatment will also be captured into the CRFs.

The following Intake and collection of data will then be conducted:

- Intake Collection of:
 - Basic Demographics
 - Date of Birth (DOB), Race, Sex, Smoking Status, County/Region
 - Medications, Co-morbidities
 - CoViD-19 Test Results (Positive / Presumed Positive)
- Study Measurements:
 - Height/Wt (BMI)
 - Temperature
 - Blood Pressure
 - O₂ Saturation
 - PaO₂/FiO₂ ratio
 - Shortness of Breath (Yes / No)
 - Cough (Yes / No)
- Clinical Labs
 - Immunokine panel (TNF- α , IL-1 β , IL-6)
 - Frozen blood sample[†]
 - Leukocyte flow cytometry
 - Pro-Calcitonin

- CRP
- Ferritin
- D Dimer
- Complete hematology panel (CBC with differential)
- Comprehensive metabolic panel
- Serum or urine hCG (for any woman who might be pregnant)
- Device training: Patient receives device training on gammaCore® Sapphire device and receives first treatment with trained study staff *
 - nVNS Stimulation Supervised**
 - Study log completion: patient will record date and times of stimulations.
 - Daily Tx Log Completion
 - Oxygen Required, Oxygen level (%) based on device type (HFNC / NC / Bipap / Optiflow), Ventilator Dependence, Date and time of Ventilation, Patient discharge home, Date and time of Discharge, Survival
 - Clinical Improvement Scale
 - Adverse event assessment

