* For those patients allocated to gammaCore (nVNS), the patient will be instructed by a study physician on the gammaCore® technique. They will be instructed to use it according to the specified protocol, which will be available at bedside. Re-training on the device or study log completion can occur at any time the patient requests further instruction or clarification and/or if research staff feels re-training is necessary during supervised stimulations.

Instructions for the use of the device will be kept in each patient's room and will not be re-used for any other patient, or removed from the patient room for any reason, throughout their study participation.

Study team will provide each patient with a laminated study log for individual patient room, each day, to log their treatments. This log will be cleaned for reuse each day for each patient, then discarded per institutional policy and will not be used by any other patient. A duplicate paper study log will be located on the outside of the room, whereas a trained study investigator will transpose the data entered on the log from the patient's room, onto a CRF, with their signature and date, each day while patient is on study.

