7.2.2 Clinical Investigation Flow Chart

Procedures and outcome measures will be collected as described in the clinical investigation flow chart shown in Table 1.

Table 1 Clinical Investigation Flow Chart

Protocol requirements	Study Visit (D=Day)								
	Admission/ D0	D1	D2	D3	D4	D5	D6	D7	Study Termination ^e
Informed Consent	X								
Inclusion/ Exclusion criteria	X								
Randomization	X								
Complete physical exam	X								
Enter Device #	X								
Intake ^a	X								
Study Measurements ^b	X	X	X	X	X	X	X	X	X
Pro-Calcitonin, C-reactive protein, ferritin, D-dimer, CBC w/dif	X (+ serum/urine hCG for women who may be pregnant)	X		X		X		X	X
Comprehensive metabolic panel	X			X		X		X	X
Study labs drawn before 10am (Frozen blood sample, Immunokine panel (Luminex) including (TNF- α , IL-1 β , IL-6), Leukocyte flow cytometry		X	X	X		X		X	

Clinical Investigation Plan

	Study Visit (D=Day)									
Protocol requirements	Admission/ D0	D1	D2	D3	D4	D5	D6	D7	Study Termination ^e	
Device training ^c	X									
nVNS Stimulation Supervised ^c	X	X								
VNS Stimulation ^c		3X +prn	X							
Clinical Improvement Scale	X	X	X	X	X	X	X	X	X	
Daily Tx Log completed ^d	X	X	X	X	X	X	X	X	X	
Concomitant medications	X	X	X	X	X	X	X	X	X	
Adverse Event	X	X	X	X	X	X	X	X	X	

- ^a Includes collection of basic demographics (DOB, Race, Sex, Smoking Status, County/Region), medications, comorbidities CoViD-19 test results)
- ^b Includes height/weight (BMI), temperature, blood pressure, O₂ saturation, PaO₂/FiO₂ ratio, shortness of breath assessment, cough assessment
- ^c For the active study arm. Includes record of treatment (time and number of doses administered)
- ^d The following parameters will be recorded daily: Oxygen dependence & data, ventilator dependence & data, discharge data, survival, device treatment record (active study arm only)
- ^e Study completion will be determined by discharge, transition to mechanical ventilation and/or if the patient is unable to continue

7.3 Discussion and Justification of Clinical Investigation Design, Including the Choice of Control Groups

The study design (randomized, including a control group) was chosen to evaluate the usefulness of the gammaCore® Sapphire device for symptom improvement in patients suffering CoViD-19 related respiratory distress compared to standardized institution treatment only.

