During hospitalization, the study patients, if able, will administer gammaCore® as prescribed for all acute respiratory attacks or shortness of breath, and also prophylactically. If patients are unable, study personnel may assist.

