7.10.1.1 Data Sets to be Analysed

The intention to treat (ITT) population includes all randomized subjects with at least 1 verified treatment post-training during study period. The ITT population will be analyzed using the subject's randomized treatment regardless of which treatment the subject actually received.

Subjects with major protocol deviations will be excluded from the per-protocol (PP) analysis set. Subjects not taking the study treatment in the prescribed manner more than 33% of the time will be excluded from the PP analysis set. Additional subjects with exclusionary protocol deviations will be identified prior to database finalization and unblinding. Analyses for the PP will be conducted according to the randomized treatment.

All subjects entering the study will be included in the safety population. Analyses for safety population will be conducted according to the treatment actually received.

Definitions

Generally, a baseline measurement refers to the last non-missing assessment made before the first administration of study treatment (at e.g. screening and baseline).

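### The ITT entry condition in 7.10.1.1 is undefined for controls and, if waived for them, permits post-randomisation exclusion in the active arm only

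*Combined protocol and SAP*

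**What the plan says.** Section 7.10.1.1 sets the entry rule: "The intention to treat (ITT) population includes all randomized subjects with at least 1 verified treatment post-training during study period". The next sentence there says that this population is analysed by randomised arm, whatever treatment was received. The safety population takes everyone who enters but is analysed by treatment received.

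On who is trained and treated:
- The synopsis says of the control arm: "SoC: No Administration of gammaCore".
- Section 7.2.1.1 ties instruction to allocation: "For those patients allocated to gammaCore (nVNS), the patient will be instructed by a study physician on the gammaCore® technique".
- In the flow chart (Table 1, section 7.2.2), footnote c is attached to the device training row and to both stimulation rows. It reads: "For the active study arm. Includes record of treatment (time and number of doses administered".
- Two places do not name an arm. Section 7.2 says: "Once qualified, the patient shall be trained on the use of gammaCore® and provided an initial treatment". The Day 0 list in 7.2.1.1 says: "Device training: Patient receives device training on gammaCore® Sapphire device and receives first treatment with trained study staff"; the synopsis has the same item.

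Section 7.10.1.2 calls all between-arm comparisons nominal. Sections 7.10.1 and 7.10.1.3 leave the detail of the analyses to a separate statistical analysis plan.

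**The concern.** An intention-to-treat set is meant to keep the groups that randomisation formed. Here entry depends on something that happens after randomisation and that, by design, happens in one arm only. The rule therefore has no workable meaning for a control. The obvious informal repair, admitting all controls and applying the condition to active patients, makes the exclusion one-sided.

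What is at stake is the claim that a set labelled ITT preserves the randomised comparison. With at most 30 patients per arm, one patient removed from one side visibly moves a proportion. Nominal status removes the inferential claim, but it does not protect the estimates and intervals that will still be presented.

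**Working it through.** The plan gives no figure for the size of the ITT set, so there is none to reproduce. The only check available is the planned enrolment in 7.4.1: 30 + 30 = 60, which agrees.

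**Reading the sections together**

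1. *Order of events.* Section 7.2 places randomisation before baseline measurements, and training and the first treatment follow. The entry condition is therefore a post-randomisation one.
2. *Who can meet it.* The synopsis, 7.2.1.1 and footnote c of Table 1 confine training and stimulation to the active arm. The sentences that say only "the patient" do not give a control a treatment after training. Section 7.10.1.1 uses the word treatment for both arms, but even if standard of care counted as a treatment, the post-training qualifier would have nothing to refer to in a control.
3. *Literal reading.* At full enrolment up to 30 of 30 active patients and 0 of 30 controls qualify. This defeats the between-arm aim in sections 6 and 7.7.2, so it cannot be meant.
4. *Waived for controls.* The sets become 30 − k active patients and 30 controls, where k is the number of active patients without a qualifying treatment.
5. *Does another sentence repair it?* The by-randomised-arm sentence fixes the arm of patients already admitted and does not admit anyone. The safety set keeps everyone but groups by treatment received, so it is not a substitute for the randomised comparison.
6. *How large might k be?* This depends on whether the supervised Day 0 treatment counts. Section 7.2 puts that treatment after training. Table 1 gives device training and supervised stimulation separate rows, both marked on Day 0. Both support counting it. Against that, 7.2.1.1 and the synopsis list the first treatment inside the device training item. Section 7.10.1.1 does not say.

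**Illustration (k and the event counts are assumptions; the documents give none)**

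Take no true effect, e events among 30 in each arm, the condition waived for controls, and k active patients excluded, of whom j had the event. The risk ratio is RR = [(e − j)/(30 − k)] ÷ (e/30).

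- k = 0: RR = 1.00 for any e.
- k = 1, j = 1, e = 6: 5/29 = 17.2% against 6/30 = 20.0%; RR 0.86, difference −2.8 points.
- k = 1, j = 0, e = 6: 6/29 = 20.7% against 20.0%; RR 1.03, difference +0.7 points.

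Range for k = 1 over e = 3 to 9:

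| e per arm | Excluded patient had the event | Excluded patient did not |
|---|---|---|
| 3 | 2/29 vs 3/30: RR 0.69, −3.1 points | 3/29 vs 3/30: RR 1.03, +0.3 points |
| 6 | 5/29 vs 6/30: RR 0.86, −2.8 points | 6/29 vs 6/30: RR 1.03, +0.7 points |
| 9 | 8/29 vs 9/30: RR 0.92, −2.4 points | 9/29 vs 9/30: RR 1.03, +1.0 points |

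If ITT is everyone randomised by allocated arm, the sets are 30 and 30, and equal event counts give RR 1.00.

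**The case against.** The strongest reply is that hardly anyone would be excluded. If Day 0 counts, as 7.2 and Table 1 suggest, an active patient drops out only by receiving neither the supervised first treatment nor any later one. These are inpatients who agreed to use the device as an entry criterion. Section 7.3 says: "If patients are unable, study personnel may assist", and 7.6 lets trained research staff give the treatment with the patient's permission. This stands, and it makes zero or very few exclusions the likely outcome.

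It is also true that comparisons are nominal, that no section assigns any between-arm summary to the ITT set, and that the separate analysis plan may say more. One patient's displacement is small beside the imprecision: for 5/29 against 6/30, the approximate 95% interval for the risk ratio is 0.30 to 2.5 (log method). All of this limits the consequence. None of it supplies an entry rule for controls, and if the separate plan corrects the definition, the protocol text would conflict with it and still need amending.

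Two stronger readings are tempting. A reader might infer that the trial has no ITT control group at all. That follows only from a literal reading that contradicts the stated aims. A reader might also infer that the rule removes early failures and so flatters the device, since ventilation ends participation under 7.2.1.5. The documents do not support that: it relies on Day 0 not counting, discharge ends participation too and would shift the result the other way, and nothing indicates how many patients would be affected.

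**Conclusion.** The definition is wrong as written. It cannot be applied to controls, and waiving it for them leaves a set that need not match the groups as randomised. Confidence is high for the wording defect only. The size and direction of any bias cannot be determined from the documents. Exclusions are probably none or very few, in which case the results would be unchanged or almost so. The risk ratios of 0.86 and 1.03 show what one exclusion could do under an assumed 6/30 events per arm; they do not predict a bias. The point is worth correcting because the label ITT promises something that the definition does not deliver, and the correction is nearly free.

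**What to change.** 1. In 7.10.1.1, define ITT as all randomised patients, analysed in the arm to which they were randomised, whether or not any device treatment was given.
2. Put any verified-treatment condition in a separately named, supportive set, and state whether the supervised Day 0 treatment qualifies.
3. State that ventilation, discharge and death in hospital are recorded, consent permitting, for randomised patients who never start the device. Reconcile this with 7.2.1.5, which ends the study when a patient is unable to continue, and with 7.4.4, which allows withdrawal from assessments.

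The cost is a wording change plus a little outcome collection from hospital records for any such patients. The wording of 7.10.2 on partial data, and follow-up after a patient stops the device, are separate issues: a patient who stops after one qualifying treatment is already in the set.

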1 SYNOPSIS

CLINICAL INVESTIGATION TITLE: A Prospective, Randomized, Controlled Study Assessing Vagus Nerve Stimulation in CoViD-19 Respiratory Symptoms (SAVIOR II)

CLINICAL INVESTIGATION CODE:

2020-132-AGH

CLINICAL INVESTIGATIONAL MEDICAL DEVICE(S):

gammaCore Sapphire® (non-invasive vagus nerve stimulator)

OBJECTIVES:

The aims of this study are to summarize and compare the incidence of clinical events and pro-inflammatory cytokine levels in patients randomized to use of gammaCore Sapphire plus standard of care vs standard of care alone in patients hospitalized for CoViD-19. In addition, this study is intended to demonstrate the safety of gammaCore Sapphire use in patients hospitalized for CoViD-19.

Specific clinical events to be summarized include, but are not limited to:

- Changes in oxygen support requirements (no oxygen support, low-flow oxygen support, nasal high-flow oxygen support, noninvasive mechanical ventilation, and invasive mechanical ventilation)
- Changes in O₂ saturation
- PaO₂/FiO₂ ratio
- Proportion of subjects requiring mechanical ventilation
- Days to onset of mechanical ventilation
- Live discharge from the hospital
- Patient length of stay
- Mortality
- Shortness of Breath
- Clinical improvement Scale

Specific laboratory measurements to be summarized include, but are not limited to:

- TNF- α
- IL-1 β
- IL-6
- CRP
- Ferritin
- D Dimer

- Pro-Calcitonin

OVERALL CLINICAL INVESTIGATION DESIGN:

The study is a prospective, randomized, controlled investigation designed for comparison of two groups for the reduction of respiratory distress in a CoViD-19 population, using gammaCore Sapphire® (nVNS) plus standard of care (active) vs. standard of care alone (SoC), the control group. The gammaCore® (nVNS) treatments will be used acutely and prophylactically.

Prophylactic

Administer one treatment of gammaCore®, scheduled three times a day (morning, mid-day and 1 hour before bed at night)

One treatment is defined as 2 consecutive doses (stimulations). Each dose delivers a 2-minute stimulation. One dose is applied to the left side of the neck, then one is applied to the right side

SoC: No Administration of gammaCore®

AND

Acute respiratory failure (w/hypoxia) or Shortness of breath

Administer one treatment of gammaCore® for acute treatment of shortness of breath (as needed, up to nine times a day)

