7 DESIGN OF THE CLINICAL INVESTIGATION

7.1 Overall Clinical Investigation Design

The study is a prospective, randomized, control investigation designed for comparison of two groups for the reduction of respiratory distress in a CoViD-19 population, using gammaCore® Sapphire plus standard of care (active) vs. standard of care alone (SoC), the control group. The gammaCore® treatments will be used acutely and prophylactically.

Figure 1 Overall Design

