7.10.2 Handling of Drop-outs and Missing Data

Outliers will be included in summary tables and listings, and will not be handled separately. Available data from prematurely withdrawn patients will be included in the analysis as far as possible. If data are only partially completed, the available data will be reported as an per protocol evaluation

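### The 33% adherence exclusion can remove only device-arm patients, so the per-protocol comparison can be biased, plausibly towards the device, and the reference to unblinding gives no protection

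*Combined protocol and SAP*

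**What the plan says.** Section 7.10.1.1 builds the per-protocol set by three exclusions: major protocol deviations, an adherence rule, and a further group to be named later.

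- The adherence rule excludes "Subjects not taking the study treatment in the prescribed manner more than 33% of the time".
- The later group: "Additional subjects with exclusionary protocol deviations will be identified prior to database finalization and unblinding".

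The set is then analysed by randomised arm. The same section admits a patient to the intention-to-treat set only after at least one verified treatment following training.

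Section 7.1 sets device plus standard of care "vs. standard of care alone (SoC), the control group", and the synopsis states for that group "SoC: No Administration of gammaCore". In the flow chart (section 7.2.2) the footnote on training and stimulation reads "For the active study arm. Includes record of treatment (time and number of doses administered". No sham is described, and neither is masking of patients, staff, assessors or analysts.

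Section 7.10.2 adds that where data are only partly complete, "the available data will be reported as an per protocol evaluation".

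**The concern.** A control patient has no study treatment to miss, so the adherence rule cannot remove one. Randomisation made the two arms comparable as allocated. Once one arm is trimmed by behaviour after randomisation and the other is not, that protection is lost. If the device patients who drop out of the set have a different prognosis from those who stay, the comparison shows a difference that the device did not cause.

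There is reason to expect such a link. Section 7.2.1.1 lets scheduled sessions continue if the patient remains stable, where possible, and lets acute sessions resume once the patient is stable again. Missed sessions may therefore cluster in patients who are getting worse, and the plan does not say whether these pauses count against adherence.

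The safeguard on the additional exclusions is weaker than it looks. With nothing blinded, whoever names those patients can know both arm and outcome. The safeguard sentence covers only the additional exclusions and does not expressly reach the 33% rule.

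**Working it through.** **Inputs from the protocol.** Allocation is 1:1, with up to 30 patients per arm (section 7.4.1). Three treatments a day are scheduled, and acute treatments are as needed (section 7.2.1.1). Section 7.10.3 says that no power analysis was done. The protocol gives no adherence, exclusion or ventilation rate, so there is no planned figure to reproduce and the rates below are assumptions.

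**Step 1: which arm can lose patients.** The adherence rule needs a prescribed study treatment and a record of its use. Both exist in the device arm only. Major deviations can occur in either arm, but that does not offset a rule that acts on one.

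**Step 2: how large the distortion could be.** Let *p* be the risk of ventilation in both arms (no true effect), *a* the chance that a ventilated device patient is excluded, and *b* the chance for other device patients. Controls are left untouched. Then

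device risk in the per-protocol set = p(1−a) / [p(1−a) + (1−p)(1−b)]

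and the odds ratio against controls is (1−a)/(1−b), whatever *p* is. With p = 0.20:

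| a | b | Device risk in the per-protocol set | Control risk | Difference (points) | Odds ratio |
|---|---|---|---|---|---|
| 60% | 20% | 0.08/0.72 = 11.1% | 20% | −8.9 | 0.50 |
| 50% | 20% | 0.10/0.74 = 13.5% | 20% | −6.5 | 0.625 |
| 40% | 20% | 0.12/0.76 = 15.8% | 20% | −4.2 | 0.75 |
| 20% | 20% | 0.16/0.80 = 20.0% | 20% | 0 | 1.00 |
| 10% | 30% | 0.18/0.74 = 24.3% | 20% | +4.3 | 1.29 |

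In the second row, 30 device patients with 6 ventilated lose on average 3 of the 6 and 4.8 of the other 24. That leaves about 22 patients, 3 of them ventilated. The sign depends only on whether *a* exceeds *b*. A simulation at 30 per arm agrees with the formula: the mean difference was −7.8 points for a = 50%, b = 10%; 0.0 for 20% and 20%; and +4.4 for 10% and 30%.

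**Step 3: whom the threshold catches.** I read the rule as excluding patients who miss more than 33% of sessions, and count scheduled sessions only. One missed session out of three is 33.3%, which already exceeds the limit. Suppose each session is missed at random with probability 20%, regardless of health. The chance of exclusion after one treatment day is 1 − 0.8³ = 48.8%. The binomial tail gives 26.2% at three days, 10.9% at seven and 6.1% at ten. The rule therefore falls most heavily on short stays, which include early discharge as well as early ventilation.

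**Step 4: the safeguard.** It has two parts, database finalization and unblinding. The first is a real time limit. The second has nothing to refer to, because no blinding is described.

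**The case against.** A reader might infer that the per-protocol comparison must favour the device and would show a benefit from an inert one. The documents do not support that. They give no adherence or outcome rates. Study staff may assist or give the treatment (sections 7.3 and 7.6). Use is recorded only on hospital days without mechanical ventilation (section 7.2), and ventilation ends the study, so sessions after it are not counted as missed. A patient who pauses as section 7.2.1.1 allows may still count as treated in the prescribed manner. Short-stay patients who did well can also be removed. The sign can be zero or reversed, as the last two rows of the table show.

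Nor is the whole safeguard void, since the database-finalization limit stands. Section 7.10.2 does not help to establish a direction: it could bring incomplete patients back into a per-protocol evaluation. It is unclear wording that sits badly with section 7.10.1.1.

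The consequence is also limited. Section 7.10.1.2 makes all between-arm comparisons nominal, the per-protocol set is not named as primary, and fuller detail is deferred to a separate SAP. With about 22 device patients against 30 controls, the 95% interval for the risk difference is roughly ±20 points, wider than any bias in the table.

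All of this stands and limits the weight of the point. It does not remove it. Calling a comparison nominal deals with error control and leaves bias in the estimate untouched. Section 7.10.1.2 still allows intervals and p-values, and section 7.13 foresees publication.

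**Conclusion.** The point holds as a structural defect of uncertain direction. The adherence exclusion acts on one arm by design, so randomisation does not protect the per-protocol comparison. Bias towards the device is plausible, because continued use is tied to stability. Under the assumed rates with no true effect, the distortion runs from 8.9 points in favour of the device, through none, to 4.3 points against it. A bias of unknown sign that may reach several points is enough to make the comparison unreliable as evidence of a device effect. The unblinding half of the safeguard is empty; the remaining time limit does not conceal arm or outcome.

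The intention-to-treat set as defined is not a clean fallback. Its requirement of one verified treatment is also a device-only condition: read literally it drops every control, and otherwise it drops only device patients who were never treated. The change should be made, but the nominal status of the comparisons keeps this short of a critical fault.

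**What to change.** In section 7.10.1.1 and in the separate SAP:

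1. Base every between-arm comparison on all randomised patients, as randomised, and remove the condition of at least one verified treatment.
2. Use the adherence-trimmed set only to describe the device arm. If an arm comparison in it is kept, label it supportive and open to selection bias.
3. Count adherence on scheduled sessions only, since as-needed use has no fixed denominator. State whether pauses that the protocol permits count as missed.
4. Settle any other exclusions before database finalization, from a listing with arm and outcome removed, and delete the reference to unblinding.
5. Reconcile the use of per protocol in section 7.10.2 with the definition in section 7.10.1.1.

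A complier-average estimate (the all-randomised difference divided by the proportion adherent) is not a good substitute. It assumes no device effect in non-adherers. Here a patient classed as non-adherent may have taken up to about two-thirds of the scheduled sessions plus acute treatments, so partly treated patients would be counted as untreated.

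The cost is a change of wording and the preparation of one masked listing. The statistical price is that the all-randomised estimate is diluted by non-adherence.
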